#### ***Adverse events***

AEs will be coded using MedDRA. The number (%) of participants experiencing a TEAE (including SAEs, AESIs, and AEs leading to premature discontinuation of study treatment) will be summarized by SOC and/or PT, and maximum intensity. A participant with multiple occurrences of an AE is counted only once in the AE category (e.g., SOC, PT).

#### ***Vital signs and electrocardiograms during post-dose cardiac monitoring on Day 1***

On Day 1, observed values and changes from baseline to all post-dose assessments in vital signs (SBP and DBP) and for 12-lead ECG variables, including HR and QTcB and QTcF intervals will be summarized by hourly timepoint. The number (%) of participants having a marked ECG abnormality will be tabulated on Day 1. The number of participants discharged at 12 h will be summarized for Day 1. For participants not discharged, reasons for not being discharged will be summarized.

The number of participants who discontinue study treatment after 12 h will also be summarized.

#### ***Vital signs and body weight***

Observed values and changes from baseline to all scheduled post-baseline visits in vital signs (SBP and DBP) and body weight will be summarized. Treatment-emergent notable BP abnormalities will be summarized.

#### ***Electrocardiograms***

Observed values and changes from baseline to all scheduled post-baseline visits for each 12-lead ECG variable (HR and the PR, QRS, QTcB, and QTcF intervals) will be summarized. The number (%) of participants with a marked ECG abnormality will be tabulated.

### ***Laboratory data***

Observed and change from baseline laboratory variables for hematology, blood chemistry, and urinalysis for all scheduled post-baseline visits will be summarized. The number (%) of participants with a marked laboratory abnormality (see Appendix 13) will be tabulated.

#### **9.2.2 Analysis of pharmacokinetic endpoints**

PK analyses will be performed using the PKS.

Plasma concentrations of cenerimod will be listed by participant and scheduled time point of blood sampling. For samples collected on Day 1/2 and at Month 2, when PK profiles are obtained, elapsed actual times will be displayed, too. Elapsed actual time in hours is defined as the number of hours elapsed from date and time of last study treatment intake to actual date and time of sampling recorded in the eCRF.

Cenerimod plasma concentrations will be summarized per scheduled timepoint by using the number of observations, arithmetic mean, minimum, median, maximum, SD, etc.. Concentrations reported as BLQ will be set to zero.

The arithmetic mean  $\pm$  SD for the cenerimod plasma concentrations will be represented graphically over time for the PK profiles obtained during the first dosing interval (i.e., pre-dose, 1, 2, 3, 4, 5, 6, 7, 8, 10, 12 and 24 h after dosing on Day 1) and at Month 2 (i.e., pre-dose, 1, 2, 3, 4, 5, 6, 7, 8, 10, 12 and 24 h after the dosing at Month 2). In addition, the arithmetic mean  $\pm$  SD for all pre-dose (trough) cenerimod plasma concentrations will be displayed graphically per visit.

PK parameters of cenerimod (AUC,  $C_{max}$ ,  $t_{max}^*$ , and AI) will be determined by non-compartmental methods by the responsible Clinical Pharmacologist using Professional WinNonlin version 8.4 or higher, Certara USA Inc and calculated based on the actual blood sampling time points. It is assumed that AUC and  $C_{max}$  are log-normally distributed [Julious 2000]. PK parameters will be listed by participant displaying the dosing interval (i.e., Day 1/2: first dosing interval, Month 2: dosing interval at steady-state conditions) and summarized by dosing interval, with arithmetic mean, minimum, median, maximum, SD, SE, geometric mean, coefficient of variation between participants in %, and 95% CIs of arithmetic and geometric means.

\*For  $t_{max}$ , the geometric mean and its 95% CI and coefficient of variation will not be calculated.

If appropriate, the steady-state PK parameters such as  $C_{min,ss}$ , etc. will be derived and analyzed similarly as above.

Further details of these analyses will be provided in the SAP.

### **9.2.3 Analysis of PD endpoints**

Lymphocyte count analyses will be performed using the PDS. Observed and change from baseline values for all scheduled post-baseline visits will be summarized. PD parameters will be calculated and summarized based on Lymphocyte counts, the details of which will be provided in the SAP.

A listing of lymphocyte counts by participant will be produced using the PDS.

### **9.2.4 Analysis of efficacy endpoints**

The following variables will be descriptively analyzed and summarized by month using the SS.

- The observed mSLEDAI-2K total score and change from baseline  
Please refer to Appendix 6 for the detailed information.
- Observed SRI-4 response.  
A participant will be assessed as a SRI-4 responder if they meet ALL the below criteria:
  1. Reduction from baseline of at least 4 points in the mSLEDAI-2K;  
and
  2. No new BILAG A organ domain score and no more than one new BILAG B organ domain score compared with baseline;  
and
  3. No increase of more than 0.3 points on the PGA Score since baseline;

If 1 of the 3 components is missing, the SRI-4 response will be missing for this assessment, unless 1 of the non-missing components is not met. In that case, the participant will be assigned a non-response status for SRI-4.

- Observed BICLA response.  
A participant will be assessed as a BICLA responder if they meet ALL the below criteria:
  - 1) Improvement from baseline in disease activity as measured by BILAG-2004. Improvement is defined as a reduction of all baseline BILAG-2004 A to B/C/D and baseline BILAG-2004 B to C/D and no BILAG-2004 worsening in other organ systems, where worsening is defined as  $\geq 1$  new BILAG-2004 A or  $\geq 2$  new BILAG-2004 B.

- 2) No worsening from baseline in mSLEDAI-2K score, where worsening is defined as an increase from baseline of > 0 points.
- 3) No worsening from baseline in the participant's lupus disease activity, where worsening is defined as an increase of 0.3 points or more on a 3-point PGA VAS score.
- 4) No discontinuation of study treatment.

If 1 of the 4 components is missing, the BICLA response will be missing for this assessment, unless 1 of the non-missing components is not met. In that case, the participant will be assigned a non-response status for BICLA.

- Response on CLASI from baseline to Month 12.  
Please refer to Appendix 10 for the detailed information.
- Change from baseline in tender and swollen joints.

The total tender joint count will be derived at each assessment, by summing the number of tender joints (= 1) as derived above. The total tender joint count values range from 0 to 28. If at least one joint was not assessed for tenderness or was not evaluable, the total tender joint count will be missing.

The total swollen joint count will be derived at each assessment in the same manner as for tender joint count. The total swollen joint count values range from 0 to 28.

- Changes in OCS dosage from baseline to Month 12.

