### 6.2.2.1 CS burst conditions of use

#### From Visit 2 to Visit 10

Participants who experienced increased SLE disease activity may receive *one* CS burst (after study visit assessments). Only one burst can be administered between Visit 2 and Visit 10, as follows:

- OCS dose increase up to a maximum daily dose of 40 mg/day prednisone or equivalent [see Appendix 12] up to a total of 14 days. This OCS increase must be fully administered and tapered to less than or equal to the Day 1 (Visit 2) dose by no later than Visit 10.

*or*
- Intramuscular methylprednisolone ( $\leq$  80 mg or equivalent) administered as a single dose.

*or*
- A maximum of 2 intra-articular / tendon sheath / bursal injections (for a total methylprednisolone  $\leq$  80 mg or equivalent) at the same visit.

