### **6.2.3      Forbidden concomitant therapy**

The following concomitant therapies are forbidden during the treatment period and until 6 months after last study treatment intake. Initiation of any of these medications will result in the permanent discontinuation of study treatment.

- Immunosuppressive agents not listed in allowed concomitant medications, such as cyclophosphamide, cyclosporine, voclosporin, leflunomide, sirolimus, tacrolimus, etc.
- Immunosuppressive or immunomodulatory biological agents (e.g., i.v. immunoglobulin, anifrolumab, rituximab).
- S1P receptor modulators other than cenerimod.
- $\beta$ -blockers, diltiazem, verapamil, digoxin, digitoxin, or any other anti-arrhythmic or HR-lowering therapy [list of drugs provided in Appendix 3].
- QT-prolonging drugs with known risk of torsade de pointes [list of drugs provided in Appendix 4].
- Vaccination with live vaccines.
- Inhibitors of the breast cancer resistance protein transporter: curcumin, cyclosporine, eltrombopag, elacridar, gefitinib, teriflunomide.
- Cannabidiol and other derivatives of marijuana.
- Investigational agents.

**Note:** due to the long half-life of cenerimod, in the event of permanent discontinuation from study treatment for any reason, participants should not receive any of the forbidden

therapies during the follow-up period of 6 months after last study treatment intake, unless clinically indicated in the judgment of the investigator.

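### SRI-4, unlike BICLA in the same section, has no discontinuation criterion, so a participant who improves off cenerimod on another therapy counts as a Month 12 SRI-4 responder

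*Combined protocol and SAP*

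**What the plan says.** Section 9.2.4 summarises SRI-4 by month in the safety analysis set. The rule opens: "A participant will be assessed as a SRI-4 responder if they meet ALL the below criteria". The three criteria are:

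- "Reduction from baseline of at least 4 points in the mSLEDAI-2K"
- "No new BILAG A organ domain score and no more than one new BILAG B organ domain score compared with baseline"
- "No increase of more than 0.3 points on the PGA Score since baseline"

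The only further rule is for missing data: "If 1 of the 3 components is missing, the SRI-4 response will be missing for this assessment", with non-response assigned if an available component already fails.

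BICLA follows in the same section. It has its own BILAG, mSLEDAI-2K and PGA criteria, then a fourth, "No discontinuation of study treatment", and a parallel missing-data rule.

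Four other places decide who gets scored:

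- Section 9.2 uses all available data unless otherwise specified. It makes no cut at discontinuation.
- Section 4.1.1 and Table 3 keep participants who stop at or before Month 6 on the monthly schedule to Month 12, with mSLEDAI-2K, BILAG and PGA collected.
- Sections 5.8.1.9 and 6.2.3 require permanent discontinuation if a forbidden therapy is started. After a stop for any reason, these therapies are to be avoided for six months "unless clinically indicated in the judgment of the investigator".
- Section 6.2.2.1 allows a corticosteroid burst for increased disease activity: "Only one burst can be administered between Visit 2 and Visit 10".

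**The concern.** The efficacy objective is to describe, preliminarily, what cenerimod 4 mg does in Chinese participants. Section 3.2 accepts that there is no placebo group and that values will be compared with baseline. In that setting, improvement produced by a replacement therapy cannot be separated from improvement produced by cenerimod. A rule that counts both as response therefore favours the drug.

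The two composites are also scored on different principles. BICLA treats stopping as failure; SRI-4 ignores it. Section 3.2 says that several efficacy endpoints are included partly so that the assessments can check one another and be compared with other studies. If the same participant is an SRI-4 responder and a BICLA non-responder only because of criterion 4, the disagreement reflects the scoring rule and not the disease. At about 15 participants, one such case is visible in the table.

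**Working it through.** The plan gives no response rate, discontinuation rate or power calculation, so there is no figure of its own to reproduce. The check has four steps.

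**1. Run one profile through both rules.** Take a participant who stopped cenerimod before Month 6, started another immunosuppressant, and at Month 12 has mSLEDAI-2K down 6 points, no new BILAG A or B, all baseline A and B grades improved, and PGA down 0.5.

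| Rule | BILAG | mSLEDAI-2K | PGA | Discontinuation | Result |
|---|---|---|---|---|---|
| SRI-4 | no new A, no new B: met | −6, at least 4 down: met | −0.5, not above +0.3: met | no criterion | responder |
| BICLA | improved, none worse: met | no increase: met | no increase of 0.3 or more: met | stopped: failed | non-responder |

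**2. How far off drug can a Month 12 responder be?** Inputs are the half-life of 33 days (Sections 2.2 and 5.5.2) and months of 30 days (Table 2). The remaining fraction of exposure is 0.5^(days/33), assuming simple exponential decline.

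- Stop at Month 6: 360 − 180 = 180 days; 180/33 = 5.5 half-lives; about 2.3% remains.
- Stop at Month 1: 360 − 30 = 330 days; 330/33 = 10 half-lives; about 0.1% remains.

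The early stopper also passes the six-month restriction on forbidden therapy at Month 7 (1 + 6), and is still scored for five more months.

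**3. Which stoppers are affected at Month 12?** Those who stop at or before Month 6 have all three components scheduled at Month 12. Those who stop in Months 7 to 12 move to the post-treatment follow-up visits, where Table 3 schedules none of the three. Their Month 12 SRI-4 would generally be missing, not a response.

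**4. Size.** With all 15 evaluable, each affected participant adds 1/15 = 6.7 points, two add 2/15 = 13.3, and three add 3/15 = 20.0. The starting counts below are assumptions; the columns show the rate after recoding 0 to 3 of the responders as non-responders.

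| Assumed observed responders | 0 | 1 | 2 | 3 |
|---|---|---|---|---|
| 6/15 | 40.0% | 33.3% | 26.7% | 20.0% |
| 8/15 | 53.3% | 46.7% | 40.0% | 33.3% |
| 10/15 | 66.7% | 60.0% | 53.3% | 46.7% |

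For scale, the exact (Clopper-Pearson) 95% interval for 8/15 is 26.6% to 78.7%, and for 6/15 it is 16.3% to 67.7%. The shift lies inside the sampling uncertainty, but it runs in one direction.

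The denominator matters too. Suppose 6 participants respond and one of the 15 is a late stopper with a missing Month 12 SRI-4. The current rule gives 6/(15 − 1) = 42.9%. With a discontinuation criterion, the late stopper fails an available component and becomes a non-responder, giving 6/15 = 40.0%.

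**The case against.** The best defence is that SRI-4 is meant as a treatment-policy summary. Section 9.2.4 calls it observed response, Section 9.2 uses all data, and Sections 5.8.1.1 and 5.8.2 deliberately keep discontinuers in follow-up to limit missing data. SRI-4 and BICLA also differ elsewhere, for example in how they treat a PGA increase of exactly 0.3. This reading is possible, but the document never states it, BICLA takes the other approach without explanation, and a treatment-policy rate is a weak guide to a drug's efficacy when there is no control arm.

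A second defence is that consequences are small: efficacy is listed as an other objective, is described only, and drives no test or decision. That stands and limits the weight of the point. Section 9 also leaves derivation algorithms to the SAP, so a rule might be placed there; none appears in the text reviewed.

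A third is that a discontinuation criterion mixes tolerability with efficacy. Someone stopped for contraception non-compliance, a low lymphocyte count or Day 1 heart rate would be scored as an efficacy failure. This also stands, and is why the current definition should be kept alongside.

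A reader might go further and infer that SRI-4 counts response during a corticosteroid burst. The document does not support that:

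- Section 6.2.2.1 places the burst after the visit's assessments and limits the oral increase to 14 days.
- From Month 2, visits are at least 30 − 7 − 7 = 16 days apart. The shortest earlier gaps are 53 − 32 = 21 days (Month 1 to Month 2) and 28 − 1 = 27 days (Day 1 to Month 1).
- Bursts are barred from Visit 10 (Day 240), which is 360 − 240 = 120 nominal days before Month 12.

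What remains is possible carry-over into monthly summaries up to about Month 8. BICLA has no burst rule either, so the contrast between the two endpoints does not extend to bursts.

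**Conclusion.** The point holds for discontinuation, and for forbidden therapy because that forces discontinuation. A participant who stops at or before Month 6 and improves on another therapy is a Month 12 SRI-4 responder and a BICLA non-responder. Compared with scoring that participant as a non-response, the plan's rule can only raise the SRI-4 rate.

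The size is 6.7 percentage points per such participant if all 15 are evaluable. The number of such participants is unknown; one to three, an assumption, would give 6.7 to 20 points. A reader might infer a definite inflated response rate, or that every discontinuer is miscounted. Neither follows: the document gives no event or response rates, and those who stop in Months 7 to 12 would mostly have a missing Month 12 value. The Month 12 endpoint is not affected by bursts.

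This is a gap in the scoring rule for a descriptive endpoint. It is worth closing because it changes a reported percentage and how SRI-4 and BICLA can be read together. It does not touch the safety, PK or PD objectives.

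**What to change.** 1. In Section 9.2.4 and the SAP, add BICLA's fourth criterion, "No discontinuation of study treatment", to SRI-4, with the same missing-data logic as BICLA. This also covers forbidden therapy started on treatment. No separate non-response rule for bursts is needed.
2. Keep the current three-component observed SRI-4 as a sensitivity summary, labelled as including assessments after discontinuation.
3. Beside the monthly SRI-4 and BICLA rates, report the number evaluable, discontinuations by reason, forbidden-therapy starts and corticosteroid bursts.

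If the sponsor prefers the observed definition as the main one, it should say so and justify the difference from BICLA.

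The cost is SAP wording, one extra summary row and a few counts; no data collection changes. There are three downsides. The SRI-4 rate will be somewhat lower. Stops for tolerability or administrative reasons will count as non-response. Late discontinuers whose Month 12 SRI-4 is now missing will become non-responders and enter the denominator. The sensitivity row and the counts by reason let a reader see each of these effects.

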##### Screening criteria

1. Signed and dated ICF prior to any study-mandated procedure.
2. Male or female Chinese participants aged from 18 to 75 years old (both inclusive) at the time of signing the ICF.
3. Diagnosis of SLE made at least 6 months prior to Screening, according to 2019 EULAR/ACR Criteria [see Appendix 2].
4. An mSLEDAI-2K score  $\geq 6$  and clinical mSLEDAI-2K score  $\geq 4$  with at least 2 points for musculoskeletal or mucocutaneous manifestations (i.e., myositis, arthritis, rash, alopecia, mucosal ulcers) [see Appendix 6].

**Note:** The mSLEDAI-2K score does not include "leukopenia". The clinical mSLEDAI-2K is the mSLEDAI-2K assessment score without the inclusion of points attributable to hematuria, proteinuria, pyuria, urinary casts, low complement, increased DNA binding, and thrombocytopenia.

5. PGA score  $\geq 1.0$  on a 0 to 3 VAS [see Appendix 9].
6. Currently treated with one or more of the following SLE background medications:
  - Antimalarials: ( $\leq 400$  mg/day hydroxychloroquine,  $\leq 500$  mg/day chloroquine,  $\leq 100$  mg/day quinacrine)
  - Mycophenolate mofetil ( $\leq 2$  g/day) / mycophenolic acid ( $\leq 1.44$  g/day)
  - Azathioprine ( $\leq 2$  mg/kg/day)
  - Methotrexate ( $\leq 25$  mg/week)
  - OCS
    - if OCS is the only SLE background medication:  $\geq 7.5$  mg/day and  $\leq 30$  mg/day prednisone or equivalent

- if OCS is not the only SLE background medication:  $\leq 30$  mg/day prednisone or equivalent
- Belimumab ( $\leq 10$  mg/kg every 4 weeks i.v. or 200 mg/week s.c.).
- Telitacicept ( $\leq 240$  mg/week subcutaneously).

Treatment with antimalarials, mycophenolate mofetil, mycophenolic acid, azathioprine, methotrexate, belimumab, or telitacicept must have been started at least 90 days prior to Screening.

Treatment with OCS must have been started at least 30 days prior to Screening.

7. For WoCBP [see definition in Section 5.5.1]:

- Negative serum pregnancy test at Screening.
- Agreement to undertake monthly urine pregnancy tests from Day 1 up to 6 months after study treatment discontinuation.
- Agreement to use a highly effective method of contraception as described in Section 5.5.2 from Screening (Visit 1) up to 6 months after study treatment discontinuation.

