#### **7.2.2.2 *British Isles Lupus Assessment Group***

The BILAG will be assessed by the investigator or delegate as per the schedule of assessments [see Section 1.3].

The scoring system for the BILAG index of disease activity is based upon the principle of the physician's intention to treat, and the main feature of the BILAG index is that disease activity in different organs/systems is reported separately. The investigator will record clinical features covered by the BILAG index of lupus disease activity and relevant data will be recorded in the BILAG form. There are 9 systems: constitutional, mucocutaneous, neuropsychiatric, musculoskeletal, cardiorespiratory, gastrointestinal, ophthalmic, renal, and hematological. Immunological data do not contribute to BILAG scores, but basic hematology and assessment of renal function determine the scores of the relevant systems [see Appendix 7]. As cenerimod causes a reduction in the peripheral blood lymphocyte count, and hence the complete WBC count, these data will not contribute to the scoring.

A score is calculated for each system depending on the clinical features present and whether they are "not present", "new", "worse", "the same" or "improving" in the last 4 weeks compared to previous assessment. Of note, the "improving" score MUST respect the following definition:

- The amount of improvement is sufficient for consideration of reduction in therapy and would not justify escalation in therapy,  
*and*
- Improvement must be **present currently and for at least 2 weeks** out of the last 4 weeks,  
*or*
- The manifestation has **completely resolved and remained absent over the whole last 1 week**.

The scoring categorizes disease activity into 5 different grades from A to E:

- Grade A represents very active disease requiring a prednisone dose of > 20 mg/day or equivalent and/or immunosuppressive drugs.
- Grade B represents moderate disease activity requiring a prednisone dose of < 20 mg/day or equivalent, topical steroids, topical immunosuppressives, antimalarials, or NSAIDs.
- Grade C represents mild stable disease.
- Grade D represents no current disease activity, but the system has been previously affected.
- Grade E represents no current or previous disease activity.

Important extensions of selected BILAG glossary and SLEDAI-2K clinical variable definitions are detailed below. Of note, protocol-specific extensions for BILAG are highlighted in italic below:

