- BILAG A or B score in the musculoskeletal organ system due to active polyarthritis, defined as follows:
  - “BILAG-2004 A”: severe arthritis (BILAG #41) with observed active synovitis in  $\geq 2$  joints with marked loss of functional range of movements and significant impairment of basic activities of daily living (ADL), that has been present on several days cumulatively over the past 4 weeks, including at the time of the Screening visit. *Basic ADLs are defined as the following activities which require assistance or assistive devices (at least 1 must be present and documented in source): ambulation, dressing, eating, toileting, grooming including bathing.*
  - “BILAG-2004 B”: moderate arthritis or tendonitis or tenosynovitis (BILAG #42) defined as tendonitis/tenosynovitis or active synovitis in  $\geq 1$  joint (observed or through history) with some loss of functional range of movements *which leads to some loss of functional range of motion as manifested by effects on instrumental ADLs (including cooking, driving, using the telephone or computer, shopping, cleaning, etc.), which has been present on several days over the last 4 weeks, including at the time of the Screening visit.*
- BILAG and SLEDAI-2K “lupus headache”: lupus headache is rare and is considered a manifestation of lupus cerebritis. Migraine, tension, or cluster headaches should not be recorded as a lupus headache. Lupus headache should only be recorded if it is disabling, lasts at least 3 days, and does not respond to narcotics. It is expected that its severity would prompt formal testing (lumbar puncture, magnetic resonance imaging, CT, etc.) and require CS and/or immunosuppressants and potentially hospitalization for treatment.

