## **9 STATISTICAL METHODS**

All statistical analyses will be conducted by the sponsor/CRO.

The SAP will provide full details of the analyses, data displays, and algorithms to be used for data derivations.

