## Appendix 6 SLEDAI-2K: Data collection sheet

Study No.: \_\_\_\_\_ Patient name: \_\_\_\_\_ Visit name: \_\_\_\_\_

d      m      yr

Enter weight in SLEDAI-2K score column if descriptor is present at the time of the visit or in the **preceding 10 days**.

SLEDAI-2K Weight	Score	Descriptor	Definition
8	_____	Seizure	Recent onset, exclude metabolic, infectious or drug causes.
8	_____	Psychosis	Altered ability to function in normal activity due to severe disturbance in the perception of reality. Include hallucinations, incoherence, marked loose associations, impoverished thought content, marked illogical thinking, bizarre, disorganized, or catatonic behavior. Exclude uremia and drug causes.
8	_____	Organic brain syndrome	Altered mental function with impaired orientation, memory, or other intellectual function, with rapid onset and fluctuating clinical features, inability to sustain attention to environment, plus at least 2 of the following: perceptual disturbance, incoherent speech, insomnia or daytime drowsiness, or increased or decreased psychomotor activity. Exclude metabolic, infectious, or drug causes.
8	_____	Visual disturbance	Retinal changes of SLE. Include cytoid bodies, retinal hemorrhages, serous exudate or hemorrhages in the choroid, or optic neuritis. Exclude hypertension, infection, or drug causes.
8	_____	Cranial nerve disorder	New onset of sensory or motor neuropathy involving cranial nerves.
8	_____	Lupus headache	Severe, persistent headache; may be migrainous, but must be nonresponsive to narcotic analgesia.
8	_____	CVA	New onset of cerebrovascular accident(s). Exclude arteriosclerosis.
8	_____	Vasculitis	Ulceration, gangrene, tender finger nodules, periungual infarction, splinter hemorrhages, or biopsy or angiogram proof of vasculitis.
4	_____	Arthritis	≥ 2 joints with pain and signs of inflammation (i.e., tenderness, swelling or effusion).
4	_____	Myositis	Proximal muscle aching/weakness, associated with elevated creatine phosphokinase/aldolase or electromyogram changes or a biopsy showing myositis.
4	_____	Urinary casts	Heme-granular or red blood cell casts.

4	_____	Hematuria	> 5 red blood cells/high power field. Exclude stone, infection or other cause.
4	_____	Proteinuria	> 0.5 gram/24 hours.
4	_____	Pyuria	> 5 white blood cells/high power field. Exclude infection.
2	_____	Rash	Inflammatory type rash.
2	_____	Alopecia	Abnormal, patchy or diffuse loss of hair.
2	_____	Mucosal ulcers	Oral or nasal ulcerations.

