2	_____	Pleurisy	Pleuritic chest pain with pleural rub or effusion, or pleural thickening.
2	_____	Pericarditis	Pericardial pain with at least 1 of the following: rub, effusion, or electrocardiogram or echocardiogram confirmation.
2	_____	Low complement	Decrease in CH50, C3, or C4 below the lower limit of normal for testing laboratory.
2	_____	Increased DNA binding	Increased DNA binding by Farr assay above normal range for testing laboratory.
1	_____	Fever	> 38 °C. Exclude infectious cause.
1	_____	Thrombocytopenia	< 100,000 platelets / $\times 10^9/L$ , exclude drug causes.
1	_____	Leukopenia	< 3,000 white blood cells / $\times 10^9/L$ , exclude drug causes.

**TOTAL SCORE:** \_\_\_\_\_

The actual scale to be used will prevail

Note that leukopenia will not be evaluated due to the mechanism of action of cenerimod.

Hematuria, proteinuria and pyuria are evaluated by dipstick at each visit assessing SLEDAI-2K. If the dipstick results are positive, urine sample will be further analyzed as clinically indicated (i.e., microscopic analysis of WBC, RBC, casts, and protein quantification).

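### BICLA in section 9.2.4 can score a participant with no baseline BILAG A or B as a responder without any improvement

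*Combined protocol and SAP*

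**What the plan says.** Section 9.2.4 makes a BICLA responder someone who meets four components:

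1. Improvement from baseline on BILAG-2004. The text then defines the term: "Improvement is defined as a reduction of all baseline BILAG-2004 A to B/C/D and baseline BILAG-2004 B to C/D", with no worsening in other systems. Worsening means at least one new A or at least two new B grades.
2. No increase in mSLEDAI-2K.
3. A PGA increase of less than 0.3.
4. No discontinuation of study treatment.

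On the population, 9.2.4 states: "The following variables will be descriptively analyzed and summarized by month using the SS". The only special rule for BICLA concerns missing components.

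The disease-activity entry criteria in section 5.2 rest on mSLEDAI-2K and PGA. Screening (criterion 4) needs a total mSLEDAI-2K of at least 6 and a clinical score of at least 4, "with at least 2 points for musculoskeletal or mucocutaneous manifestations (i.e., myositis, arthritis, rash, alopecia, mucosal ulcers"). Day 1 (criterion 8) repeats the clinical-score requirement. Neither list asks for a BILAG grade.

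Section 9 defers further detail: "The SAP will provide full details of the analyses, data displays, and algorithms to be used for data derivations".

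**The concern.** Component 1 is the only part of BICLA that demands improvement; the other three are met by standing still. Its reduction requirement applies only to systems graded A or B at baseline. With none, that requirement is empty and only the no-worsening part can fail the participant.

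Two participants who both stay exactly as they were would then be classified in opposite ways, purely because one started with an A or B and the other did not. The reported BICLA rate would mix improvement with stability. Section 3.2 says the several efficacy endpoints are there partly to allow comparison with other studies, and a mixed rate serves that purpose poorly.

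**Working it through.** The plan states no BICLA rate and gives no calculation behind its sample size of about 15, so there is no figure to reproduce. The check has three parts.

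**1. What the rule does when applied literally** (mSLEDAI-2K unchanged and treatment ongoing in every row)

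| Baseline BILAG | Later BILAG | PGA change | BICLA |
|---|---|---|---|
| C in two systems | unchanged | 0 | responder |
| C in two systems | one system C to B | +0.2 | responder |
| C in two systems | both C to B | 0 | non-responder |
| one B | unchanged | 0 | non-responder |
| one B | B to C | 0 | responder |

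Next, take every pair of baseline and later grades A to D in two systems, with mSLEDAI-2K and PGA unchanged, and count the responders in whom no grade falls. Such a profile allows no A and at most one B afterwards:

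- baseline C and C: 3 profiles
- baseline C and D: 5
- baseline D and C: 5
- baseline D and D: 8

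The total is 3 + 5 + 5 + 8 = 21. All 21 have no A or B at baseline. With a baseline A or B the count is zero, because the reduction requirement then forces a fall.

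**2. Whether such a participant can enter**

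- SLEDAI-2K arthritis (Appendix 6) scores 4 points for two or more "joints with pain and signs of inflammation (i.e., tenderness, swelling or effusion").
- Moderate arthritis, the BILAG B item in section 7.2.2.2, needs tendonitis/tenosynovitis or active synovitis in at least one joint ("observed or through history) with some loss of functional range of movements"). The BILAG form in Appendix 7 lists mild arthritis as a separate item.
- Low complement (Appendix 6) scores 2 points: "Decrease in CH50, C3, or C4 below the lower limit of normal for testing laboratory". On the BILAG side, section 7.2.2.2 says "Immunological data do not contribute to BILAG scores".

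Total mSLEDAI-2K = 4 + 2 = 6, which meets the threshold of 6. Clinical mSLEDAI-2K, which leaves out low complement, = 4. That meets the threshold of 4, with 4 musculoskeletal points against the 2 required. Criteria 4 and 8 are therefore met with no musculoskeletal A or B. The PGA criterion (at least 1.0) does not close the gap, because section 7.2.2.4 places the mark 1 at the upper limit of mild disease.

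**3. Size**

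Take 15 participants in the Safety Analysis Set, one with no baseline A or B who does not change, and r responders among the other 14.

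- Against counting that participant as a non-responder: (r + 1)/15 − r/15 = 1/15 = 6.7 points.
- Against leaving that participant out: (r + 1)/15 − r/14 = (14 − r)/210. This is 6.7 points at r = 0, 4.8 at r = 4, 3.3 at r = 7 and 0 at r = 14.

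The number of such participants, k, is not given. The next table is an illustration only. It assumes that none of the k change and that about 40% of the others respond, rounded to whole participants; neither figure comes from the documents.

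| k | As written | Counted as non-responders | Excluded |
|---|---|---|---|
| 0 | 6/15 = 40.0% | 6/15 = 40.0% | 6/15 = 40.0% |
| 1 | 7/15 = 46.7% | 6/15 = 40.0% | 6/14 = 42.9% |
| 3 | 8/15 = 53.3% | 5/15 = 33.3% | 5/12 = 41.7% |
| 5 | 9/15 = 60.0% | 4/15 = 26.7% | 4/10 = 40.0% |
| 8 | 11/15 = 73.3% | 3/15 = 20.0% | 3/7 = 42.9% |

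**The case against.** The best counter-arguments are these.

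- **The opening words of component 1 call for improvement, so a programmer could refuse response where nothing fell.** The next sentence defines improvement, and a definition normally governs. If both readings are tenable, two programmers could classify the same participant differently, which also calls for a written rule.
- **The SAP may settle it.** It may, and the fix can sit there. But the supplied text contains no such rule, although 9.2.4 already specifies BICLA down to missing components.
- **The entry example covers only one of the nine BILAG systems, and grading needs a glossary that is not supplied.** This stands. The participant must also have no A or B in the other eight systems. The example shows that the case is possible, not that it is common.
- **The population is described as moderate-to-severe, so the case may be rare.** Also fair. Section 7.2.2.2 describes grade B as moderate activity and grade C as mild stable disease. This bears on frequency but does not exclude the case, and the effect could turn out to be zero.
- **BICLA is one of six descriptive efficacy endpoints, and SRI-4 would expose the discrepancy.** The limited impact is accepted. SRI-4 needs a fall of at least 4 mSLEDAI-2K points, so an unchanged participant cannot be an SRI-4 responder. A gap between the two rates would be visible, but its cause would not be, unless baseline BILAG status were reported too.
- **Restricting the denominator is only one acceptable rule.** True. Classifying these participants as non-responders or reporting them separately would also remove the ambiguity. Counting them all as non-responders would misclassify someone who truly went from C to D, so that approach fits a sensitivity summary better than the main one.

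**Conclusion.** The concern holds. As written, the BICLA rule scores an unchanged participant as a responder when there is no A or B at baseline, and the current entry criteria and analysis set allow such a participant to be counted. The conclusion rests on the stated definition governing the opening words of component 1, and on no unseen SAP rule overriding it.

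The size is bounded per participant rather than overall: 6.7 percentage points each against non-response, and between 0 and 6.7 points for a single case against exclusion. Both figures assume 15 participants contribute and the affected one does not improve. The number affected cannot be derived from the documents. The consequence is confined to one descriptive endpoint with no hypothesis test; the primary safety, PK and PD results are unaffected. It should be corrected, but it does not threaten the trial's main purpose.

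**What to change.** Add to section 9.2.4, or to the SAP, a sentence such as: *BICLA response is assessed in participants with at least one BILAG-2004 A or B grade at baseline.* Then:

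- state that denominator at each monthly summary;
- report how many participants in the Safety Analysis Set are not evaluable for BICLA for this reason;
- add a sensitivity summary on the full set that counts them as non-responders, labelled as a conservative bound.

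The improvement definition in section 6.2.1.2.3, used for OCS changes between Visit 2 and Visit 5, has the same form and leaves the same case open. The sponsor should reconcile the two passages; no view is taken here on the clinical rule.

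The cost is one sentence and one extra summary line. BILAG is already scheduled on Day 1 (Table 2), so no new data are needed. The amendment details for version 3.0 record no participants enrolled at that date, so the rule could have been fixed then without knowledge of any results. The drawback is a denominator that may fall below 15 and a BICLA rate that may be lower.
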